1 PROTOCOL SUMMARY

1.1 SYNOPSIS

- Title:** Data-informed Stepped Care (DiSC) to Improve Adolescent HIV Outcomes (UH3): A cluster randomized trial on a Data Informed Stepped Care intervention to improve retention among adolescents living with HIV
- Grant Number:** UH3 HD096906
- Study Description:** The goal of this study is to develop, pilot and test a Data informed Stepped Care (DiSC) Intervention in a cluster randomized controlled trial (cRCT). The intervention is comprised of a system to assign adolescents living with HIV (ALHIV) to different levels of care, depending on their current and anticipated health care needs.
- Objectives*:**
- Primary objective**
- Aim 1:** To develop, adapt, pilot, and optimize implementation of a data-informed stepped care (DiSC) intervention for ALHIV HIV treatment management.
- Aim 2:** To evaluate effectiveness of the DiSC intervention on ALHIV retention in up to 24 high-volume HIV clinics in Homabay, Kisumu and Migori counties in Western Kenya.
- Secondary objectives**
- Aim 1:** To determine acceptability, feasibility, adaptability and fidelity of the DiSC intervention
- Aim 2:** To evaluate the effectiveness of the DiSC intervention on ALHIV cascade outcomes (adherence, viral suppression) and adolescent self-efficacy, health service outcomes, implementation outcomes in high volume HIV clinics in Homabay, Kisumu and Migori counties.

Endpoints*:	Primary Endpoint: % retained at 6 and 12 months Secondary Endpoints: % virally suppressed at 6 and 12 months after ART initiation, proportion with >80% adherence since last refill, % retained at 18 and 24 months, adolescent self-efficacy and correlates of retention and viral suppression. Secondary implementation outcomes: intervention reach, adoption, fidelity, acceptability, feasibility, implementation and maintenance.
Study Population:	Up to 40 Health care workers (HCW), youth, policy makers and stakeholders in adolescent HIV care (aim 1 intervention development), HCW in 2 clinics in Kenya (aim 1 pilot) 6000medical records of adolescents and young adults ages 10-24 years enrolled in HIV care, and HCW in participating facilities, Approximately 3000 HIV positive adolescents and young adults,900 caregivers of HIV positive adolescents and young adults and a 200 HCWs. (Aim 2).
Phase* or Stage:	Phase III Clinical Trial

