Failed	Unsuppressed at last measure	-Monthly visits (6 weekly for school going)	-2 weekly adherence sessions (could make some on phone) -Accelerated repeat test timeline (3 month) -Prompt switch after second test -Case manager -DOTS by HCW (or caregiver/family)	-Support group -Special treatment failure support groups -Home visit by HCW -Viremia clinics

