HCW implementation logs: These will be collected weekly and combined with information collected in annual HCW surveys to understand intervention and implementation processes in real time and service efficiency outcomes. We will specifically evaluate the percent of HCWs using the intervention, percent of adolescents in each step, percent of adolescents assigned to correct step, and percent of adolescents ‘adherent’ to services in each step. We will also collect basic information on numbers of adolescents attending clinic each week, and the number exposed to the intervention. In control sites, we will collect information on classification of adolescents as stable/unstable and offer for differentiated services.

ALHIV and caregiver satisfaction surveys: Surveys will be given to a random sample of adolescents and caregivers in intervention sites at the end of the study to evaluate satisfaction with their care.

ALHIV FGDs/IDIs: We will conduct FGDs/IDIs with adolescents in intervention sites at the end of the intervention period to determine acceptability, feasibility and satisfaction with the intervention. FGD/IDI participants will be purposively selected from adolescents in intervention clinics. We will conduct FGDs/IDIs with up to 50 people per facility.

The table below summarizes study outcomes and definitions

Summary of outcomes and definitions

Aims	Outcome type	Outcome	Definition
Aim 1	Primary	Final optimized DiSC intervention	Modified DiSC intervention with input from workshop and pilot phase
	Secondary	DiSC intervention feasibility	Suitability for everyday use and practicality

Adapted from NIH Behavioral and Social Intervention Clinical Trial Protocol Template v3.0 - 20180827

		DiSC intervention acceptability	HCW satisfaction with the intervention
		DiSC intervention adaptation and fidelity	The degree with which the intervention is modified and implemented as planned
Aim 2	Primary	Retention in care	>30 days late for a scheduled visit at 6-month intervals
	Secondary	ART adherence	Proportion of days on ART based on last dispense date
		Viral suppression	<50 copies per milliliter and a second analysis using greater than lower limit of detection
		Co-factors of retention and viral suppression	School drop-out, relationships, depressive symptoms, substance use, social support, and satisfaction with care
		ALHIV self-efficacy	Self-efficacy scales from standard questionnaires
		Health service efficiency	Client wait time

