2.1. Summary of primary and secondary outcomes

Table 1. Outcome definitions and assessment

Outcome	Indicator	Source	Timing
Primary outcome			
Retention in care	Missed visits: Not seen within 30 days of a scheduled visit.	EMR data (Visit Date, TCA)	All visits occurring during the 12-month period after the study enrollment visit*
Secondary outcomes			
Loss to follow-up	Not return to care within the 12 months study interval	EMR data (Visit Date, TCA)	All visits after the first study visit until event or end of follow-up at 12 months. Participants marked as 'transferred out' or 'died' will be censored.
Viral non-suppression	Having HIV viral load (VL) >1,000 copies/mL	NASCOP data, abstraction of paper records	All visits from enrollment to 12 months follow-up*
Receiving differentiated care	
 Long inter-visit interval Fast-track visit 	EMR data (TCA, Care Model)	All visits from enrollment to 12 months follow-up*
Adherence	Pill coverage estimated by days of dosing and inter-visit interval since last visit >80%	EMR data (Visit Date, next Visit Date, Duration)	All visits from enrollment to 12 months follow-up*

*time window up to 12 months + 30 days

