3.5. Analysis of secondary study outcomes

3.5.1. Loss to follow-up:

- Loss to follow-up will be defined as a participant missed a visit and did not return to care within the 12-month study period. The proportion of loss to follow-up during 12-month study interval (window up to 12 months +30 days) will be compared between study arms using Poisson regression with robust errors.
- Time to loss to follow-up will be compared between arms by survival curves, and death or transfers will be censored. The hazard of loss to follow-up will be compared between study arms using Cox proportional hazards regression.

3.5.2. Viral non-suppression:

- Viral non-suppression will be defined as having HIV viral loads (VL) >1,000 copies/mL. Each VL testing result will be classified as VL suppressed vs. unsuppressed. The proportion of viral non-suppression during follow-up will be compared between study arms using mixed-effects Poisson regression with random effects for facility and participant and robust standard errors.

3.5.3. Receiving differentiated care:

- Receiving differentiated care will be defined in two ways. One approach will evaluate the next visit appointment date (scheduled inter-visit interval) – visits scheduled for ≥ 3 months after visit will be considered as differentiated care, in comparison to monthly visits recommended for AYA in current guidelines. The second approach will use the variable ‘fast-track’ at each visit – ‘fast track’ visits are considered as a component of differentiated care. Two analyses will be conducted (one for long scheduled inter-visit interval and one for ‘fast track’), each will be compared between study arms using mixed-effects Poisson regression with random effects for facility and participant and robust standard errors.

3.5.4. Adherence:

- Adherence will be evaluated using the proportion of days of pill dosing over days of inter-visit interval. The level of adherence during the past inter-visit interval will be assessed at each visit. A proportion over 80% as good adherence. The dichotomized adherence will be compared between arms using mixed-effects Poisson regression with random effects for facility and participant and robust standard errors.

Table 5. Analysis of secondary study outcomes

Loss to follow-up				
	Overall	Control	Intervention	Intervention vs. control
	Count (proportion)			^a RR (95% CI) ^b HR (95% CI)
Event Person-year Cumulative incidence Incidence rate (per 100 person-years)				
Viral non-suppression				

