	Overall	Control	Intervention	Intervention vs. control
	Count (proportion) / Median (IQR)			^c RR (95% CI)
Per participant Number of viral load assays				
Over all participants Number of viral load assays Number of non-suppression results (%)				
Differentiated care: long-interval visits scheduled				
	Overall	Control	Intervention	Intervention vs. control
	Count (proportion) / Median (IQR)			^c RR (95% CI)
Per participant Number of scheduled visits				
Over all participants Number of scheduled visits Number of long-duration interval (%)				
Differentiated care: fast-track visits				
	Overall	Control	Intervention	Intervention vs. control

DiSC UH3 Statistical Analysis Plan (SAP)

	Count (proportion) / Median (IQR)			°RR (95% CI)
Per participant Number of visits with non-missing care model				
Over all participants Number of visits with non-missing care model Number of fast-track visits (%)				
Adherence				
	Overall	Control	Intervention	Intervention vs. control
	Count (proportion) / Median (IQR)			°RR (95% CI)
Per participant Number of intervals with good adherence				
Over all participants Number of intervals with good adherence Number of intervals with good adherence (%)				

^a Estimated by Poisson regression with robust errors

^b Estimated by Cox proportional hazards regression

^c Estimated by mixed-effects Poisson regression models with random effects for facility and participant and robust standard errors

*Models adjusted for any factors differing between arm with statistical significance at enrollment

Section 4. Missing data

While we will attempt to follow all participants at 12 months, we anticipate that EMR data and VL data may be incomplete for some participants might be a challenge due to participant loss to follow-up – either due to loss from care, or silent transfer to another facility. Due to the level of missingness we expect, we will not conduct any formal imputation.

Section 5. Safety monitoring

Adverse and severe adverse events, including social harms such as violence or breach of confidentiality, will be monitored as they arise, and unblinded results will be reviewed by the DSMB. The DSMB will make recommendations regarding any imbalances in safety outcomes.

SAE #	PTIDNO	Study arm	SAE description	Onset date	Duration (days / unresolved)	Onset since randomization (days)	Relatedness to study

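### The SAP scores adherence between consecutive visits, not between refills as in the protocol, so recorded visits without dispensing can bias the adherence risk ratio in either direction

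*SAP*

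**What the plan says.** **SAP.** Section 3.5.4 defines the measure: "Adherence will be evaluated using the proportion of days of pill dosing over days of inter-visit interval". It adds: "The level of adherence during the past inter-visit interval will be assessed at each visit". The adherence row of Table 1 in section 2.1 gives the indicator as "Pill coverage estimated by days of dosing and inter-visit interval since last visit >80" (per cent), covers all visits from enrollment to 12 months, and names the source as "EMR data (Visit Date, next Visit Date, Duration". The SAP does not limit the measure to refill visits, carry over pills in hand, cap the ratio, or say how a zero or blank Duration is scored. Section 4 says only that there will be no formal imputation.

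**Protocol.** The outcome table in section 8.1 defines ART adherence as "Proportion of days on ART based on last dispense date". The synopsis (1.1) lists "proportion with >80% adherence since last refill", and section 9.4.3 uses the same refill-based measure.

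**Intervention.** The sample step table in protocol 6.1.1 gives the Failed step "2 weekly adherence sessions (could make some on phone", alongside regular visits that are monthly, or 6-weekly for those in school.

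**Table shell.** In SAP Table 5, the two adherence rows over all participants read "Number of intervals with good adherence Number of intervals with good adherence", the second with a percentage. No total number of intervals is printed.

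**The concern.** Days dispensed divided by days to the next visit measures pill coverage only when each recorded visit is also a refill. A contact with no dispensing splits one refill interval into two. The first part then looks over-supplied. The second looks empty or disappears, depending on how Duration is stored.

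Visit frequency is part of what DiSC changes, both by stepping visits down and by adding support contacts. A measure that depends on the number of non-dispensing visits can therefore be wrong by different amounts in the two arms. At stake is one secondary outcome, the adherence risk ratio, which could move without any difference in pill coverage. The primary outcome, missed visits, is not affected.

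**Working it through.** The documents give no expected adherence rate or power for this outcome, so there is no planned figure to reproduce. The check applies the SAP ratio to constructed histories.

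**One adolescent, full coverage.** 30 days of pills are dispensed each month, with a no-refill session on day 14.
- Days 0 to 14: 30/14 = 214%, good.
- Days 14 to 30, Duration stored as 0: 0/16 = 0%, not good. Over a year, 12 of 24 intervals are good (50%). If half the sessions are recorded as visits, 12 of 18 are good (67%).
- Days 14 to 30, Duration blank and interval dropped: 12 of 12 are good.
- Dispensing to dispensing: 30/30 = 100%, so 12 of 12 are good.

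**One adolescent, half covered.** 30 days of pills are dispensed every 60 days, with a no-refill session on day 14.
- Blank intervals dropped: 30/14 = 214%, so 6 of 6 are good.
- Duration stored as 0: 6 of 12 are good.
- Dispensing to dispensing: 30/60 = 50%, so 0 of 6 are good.

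**Arm level, full coverage in both arms, Duration stored as 0.** Let f be the share of the DiSC arm in the Failed step, s the recorded no-refill sessions per year in that step, and n the refill visits per year for everyone else. The Failed step has 12 refills a year. Control is assumed to have no such sessions, so it scores 100%.

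Pooled share good = [12f + n(1 − f)] / [(12 + s)f + n(1 − f)]

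The value f = 0.15 is an assumption. It takes 1 − 0.85 from the 85% suppression figure in protocol 9.2, which is not a step share.

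| f | s | n | Calculation | Crude pooled ratio |
|---|---|---|---|---|
| 0.15 | 12 | 12 | 12/13.8 | 0.87 |
| 0.15 | 12 | 4 | 5.2/7.0 | 0.74 |
| 0.15 | 6 | 12 | 12/12.9 | 0.93 |
| 0.15 | 6 | 4 | 5.2/6.1 | 0.85 |
| 0.05 | 3 | 12 | 12/12.15 | 0.99 |
| 0.25 | 12 | 4 | 6/9 | 0.67 |

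The last two rows are the ends of the range for 5–25% in the step and 25–100% of sessions recorded. Averaged per participant, f = 0.15 and s = 12 give 0.15 × 0.50 + 0.85 × 1.00 = 0.925, a ratio of about 0.93.

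**The same histories under other rules.** With blank intervals dropped, or with refill-to-refill intervals, every full-coverage scenario gives 100% in both arms, a ratio of 1.00.

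**Why carry-over is also needed.** Suppose 30 days are dispensed on day 0, another 30 on day 14, and the next refill is on day 60. Sixty days of pills cover 60 days. Without carry-over the second interval scores 30/46 = 65%, not good. With the 16 days left over it scores (16 + 30)/46 = 100%.

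**The case against.** A reader might infer that the SAP scores every non-refill visit as 0%, and so will make DiSC look harmful even with perfect adherence. The documents do not support that. A 0% score needs the session to be a recorded EMR visit, nothing to be dispensed at it, Duration to be stored as 0 rather than blank, and pills in hand to be ignored. The SAP is silent on these points. Its own term, pill coverage, could be read as counting pills in hand.

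Nor do the documents show that the extra contacts will appear as EMR visits in the DiSC arm only:
- The step table is labelled a sample, and protocol 6.2.1 leaves the number of steps and the assignment system to the development workshop.
- Some sessions may be by phone.
- Protocol 1.1 and 4.3 place the intervention within routine visits, and sections 6.4 and 8.1 track delivery in separate logs.
- Control clinics give additional support as needed (protocol 4.1), so they may hold non-dispensing visits too.

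The arm-level figures also lean towards the unfavourable end. Control is fixed at 100%, and the 15% stay in the Failed step all year although steps can be re-assigned. School-going adolescents would be seen 6-weekly, not monthly. The ratios are crude, whereas the SAP fits a mixed-effects Poisson model with a participant random effect; that model was not fitted here.

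All of this stands against a claim of false harm. It does not remove the difference between SAP and protocol, or the missing rule. The SAP handles a parallel case with more care: the Table 5 denominator for fast-track visits is limited to visits with the care model recorded.

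**Conclusion.** The SAP's adherence measure departs from the protocol's dispensing-based definition and misstates coverage when a recorded visit dispenses nothing. The resulting bias in the risk ratio could run either way, depending on the number of such visits in each arm and on how Duration is stored.

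The figures are illustrations, not predictions. With full coverage in both arms, Duration stored as 0 and no such visits in control, the crude pooled ratio runs from 0.67 to 0.99 over the assumptions tried. If blank intervals are dropped, the same histories give 1.00, and poor coverage can then be hidden instead.

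The repeated Table 5 label is a separate drafting slip and does not affect the risk ratio. The derivation should be settled before results are seen, in proportion to a secondary outcome.

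**What to change.** In SAP 3.5.4 and the adherence row of Table 1 (section 2.1):
- Define the interval from one dispensing date to the next, in line with protocol 8.1 and 9.4.3, so that a non-dispensing visit neither opens nor closes an interval.
- Carry over pills in hand from early refills, and cap coverage at 100%.
- State how a zero and a blank Duration are each classified: no dispensing, or missing.

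In Table 5, change the first of the two repeated adherence rows to the number of dispensing intervals assessed.

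The cost is SAP wording and slightly more programming, using EMR fields that Table 1 already names. There will be fewer intervals per participant.

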3.4. Analysis of retention

Retention will be evaluated using an indicator of missed visits. A missed visit will be defined as a participant not seen within 30 days of a scheduled visit during follow-up since the first stepped care visit to 12 months. Each scheduled visit will be classified as missed versus not missed and analysis will use repeated measures per participant. The proportion of missed visits will be compared between study arms using mixed-effects Poisson regression with random effects for facility and participant and robust standard errors.

Sub-group analyses for retention will be performed by gender and age-group. Facility factors, including concurrent adolescent-friendly services and high/low performance will be evaluated as modifiers of intervention effectiveness.

Table 4. Analysis of missed visits

	Overall	Control	Intervention	Intervention vs. control
Missed visits per participant				^a RR (95% CI)
Median (IQR)				
Number of scheduled visits				
Number of missed visits (%)				
Missed visits over all participants				
Count (proportion)				
Number of scheduled visits				
Number of missed visits (%)				
Number of AYA ever missed a visit (%)				

^a Estimated by mixed-effects Poisson regression with random effects for facility and participant and robust standard errors

*Excluding TCA that had miss/no-miss status censored or missing

*Models adjusted for any factors differing between arm with statistical significance at enrollment

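### Adherence, and possibly viral load, is counted from the enrollment visit itself, so at least one pre-intervention record per participant can enter as an outcome

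*SAP*

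**What the plan says.** SAP Table 1 (section 2.1) gives each outcome its own counting window, and the starting points differ.

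- Retention: "All visits occurring during the 12-month period after the study enrollment visit".
- Loss to follow-up: "All visits after the first study visit until event or end of follow-up at 12 months".
- Viral non-suppression, differentiated care and adherence: "All visits from enrollment to 12 months follow-up".

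Adherence is defined as looking back in two places. The Table 1 indicator is "Pill coverage estimated by days of dosing and inter-visit interval since last visit >80" per cent, and SAP 3.5.4 says "The level of adherence during the past inter-visit interval will be assessed at each visit". The Table 1 source fields for the same outcome are "EMR data (Visit Date, next Visit Date, Duration"), which name the next visit and not the previous one.

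For viral load, SAP 3.5.2 classifies every test result and says "The proportion of viral non-suppression during follow-up will be compared between study arms". It gives no first day, no lag and no rule for a test on the day of enrollment. The retention analysis in SAP 3.4 does give follow-up a start: "during follow-up since the first stepped care visit to 12 months".

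The only covariate rule, in the footnotes to SAP Tables 4 and 5, adjusts for factors that differ significantly between arms at enrollment. The baseline list in SAP Table 3 has neither prior viral load nor prior pill coverage.

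**The concern.** Protocol 10.1.1.1 places written consent before the study intervention starts. Drug-taking in the interval that ends at the enrollment visit therefore cannot have been changed by the intervention, and a viral load drawn at that visit reflects drug-taking before it. Both are baseline values. If they are pooled with follow-up records in a model with a single arm effect, they add records in which the expected arm difference is zero and so dilute the estimate. They are also lost as baseline information, which would be useful in a trial with only 24 randomized clinics.

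Two secondary effectiveness outcomes are at stake. As the plan stands, two programmers could build different analysis sets from it and both could claim to have followed it.

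**Working it through.** **Inputs from the documents.** Regular visits are 1 to 6 months apart (Protocol 4.3). Routine viral load is tested 6 months after ART initiation and then annually (Protocol 8.1). The design contrast is 64% to 82% suppressed, with 50 records per facility, 12 facilities per arm, a clustering value of 0.10, alpha 0.05 and 80% power (SAP 2.2.2).

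**Assumptions.** The arms have equal levels before the intervention, follow-up is complete, and records are pooled with equal weight. The mixed model will weight records somewhat differently, so the results are approximate.

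**Step 1: reproduce the plan's viral load figure.** Facilities per arm = (1.960 + 0.842)² × [p1(1−p1) + p2(1−p2)] / (p2−p1)² × [1 + (m−1) × ICC] / m.

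With p1 = 0.64, p2 = 0.82, m = 50 and ICC = 0.10, this is 7.849 × 0.378 / 0.0324 × 5.9 / 50 = 10.81, which rounds up to 11. The SAP table shows 11, so the calculation reproduces. By the same method, power with 12 facilities of 50 records is 84%.

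**Step 2: share of pre-intervention adherence records.** With k intervals after enrollment and one look-back interval at enrollment, f = 1/(k+1).

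- Monthly visits: k = 12, f = 1/13 = 7.7%.
- 3-monthly visits: k = 4, f = 1/5 = 20%.
- 6-monthly visits: k = 2, f = 1/3 = 33%.

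A participant lost early contributes fewer later intervals, so f is larger for that person.

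**Step 3: effect on adherence.** The documents give no expected adherence rates, so assume good adherence of 70% in control and at baseline, and 80% under the intervention. The true RR is 0.80/0.70 = 1.143. The observed RR is [0.70f + 0.80(1−f)] / 0.70.

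| f | Observed RR |
|---|---|
| 1/13 | 1.132 |
| 1/5 | 1.114 |
| 1/3 | 1.095 |

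On the risk-difference scale, the 10 points become 9.2, 8.0 and 6.7, that is 10 × (1−f).

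**Step 4: effect on viral load (illustration only).** The share of tests falling on the enrollment date is not in the documents. The SAP contrast implies non-suppression of 36% against 18%, an RR of 0.50. The observed RR is f + (1−f) × 0.50, and the observed difference is 18 × (1−f) points.

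| f | Difference (points) | RR of non-suppression | Power, 12 × 50 | Power if these records are dropped |
|---|---|---|---|---|
| 0 | 18.0 | 0.50 | 84% | 84% |
| 7.7% | 16.6 | 0.54 | 77% | 83.5% |
| 20% | 14.4 | 0.60 | 63% | 82.6% |

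The last column keeps the 18-point contrast and reduces the records per facility to 50 × (1−f). With ICC 0.10, losing records within a facility costs little power. Diluting the contrast costs much more.

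**The case against.** The best counter-argument is that the wording does not settle the matter.

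For viral load, SAP 3.5.2 limits the comparison to follow-up, and the one place where follow-up is anchored (SAP 3.4) starts it at the first stepped care visit. A careful programmer could leave out an enrollment-day result. This stands: a reader might infer that the plan definitely counts baseline viral loads as outcomes, but the documents show only that nothing excludes them.

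For adherence, the source fields could describe a forward interval, keyed to the dispensing visit. On that reading the enrollment record yields the first interval after enrollment, and nothing is diluted. This is weaker. The same date fields can serve a backward calculation, and both definitions in words look back. It does show that the text and the fields need to be reconciled.

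The different start for retention is also natural, since a participant present at enrollment cannot have missed that visit. And the shared phrase suits differentiated care, because the next appointment given at enrollment may already reflect the intervention. The contrast between rows is therefore no sign of a deliberate choice to count baseline values.

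On baseline adjustment, the footnote rule is not limited to the Table 3 list, so prior viral load or coverage could enter if it differed significantly. That makes its use depend on a significance test and does not prespecify it. Prior values will also be missing for some: Protocol 8.1 takes viral load from the EMR only if available, and SAP Section 4 expects incomplete data.

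**Conclusion.** The point holds for adherence on the literal text, and for viral load as an ambiguity that should be closed. With equal baseline levels, the expected risk difference shrinks by the share of pre-intervention records. For adherence this is about 8% to 33% of records, depending on visit spacing, and it moves an assumed RR of 1.14 to between 1.13 and 1.10. For viral load the share is unknown, and 0.54 to 0.60 in place of 0.50 is an illustration at 7.7% to 20%.

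Three stronger readings are tempting and not supported.

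- A reader might infer that both comparisons are certain to be pulled toward no effect. Attenuation holds only in expectation; with 24 clinics a chance baseline difference could move the estimate either way. The share may also differ by arm, because the intervention changes visit spacing and the sample steps in Protocol 6.1.1 include accelerated repeat viral load testing.
- A reader might apply the 0.50-to-0.60 shift to adherence. That shift belongs to the adverse outcome. The SAP models good adherence, where the RR moves much less.
- A reader might count any baseline imbalance as false effect created by this rule. If the imbalance persists, records after enrollment carry it too, and dropping the enrollment record does not remove it. That is the reason for covariate adjustment.

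The primary outcome already starts after enrollment and is not affected.

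**What to change.** 1. In SAP Table 1 and 3.5.4, count only pill-coverage intervals that begin on or after the enrollment visit.
2. In SAP Table 1 and 3.5.2, count only viral loads drawn after the date of the enrollment visit.
3. Make the adherence definition and its source fields describe the same interval, naming the visit whose dispensed days are the numerator and the two dates that bound the denominator.
4. Leave the differentiated-care window as it is.
5. Prespecify the last viral load on or before enrollment, and the coverage for the interval ending at enrollment, as covariates in the respective models whether or not the arms differ on them, with a category for no prior value.

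The cost is SAP wording and programming, with no new data collection. At most one record per participant for each outcome moves from outcome to baseline. One limit remains: viral loads drawn soon after enrollment will still partly reflect earlier drug-taking.
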